**SHORT TITLE/ACRONYM**

Recruitment of this group will be done via the Brookes BabyLab database (3500+ registered families). Infants in this group will be matched to the other groups based on gender and family SES (i.e., parental education, household income).

The incubator and cot systems will be equipped with computers that broadcast the womb-like acoustic environment developed in WP1. A marker process will facilitate the identification of elements within these recordings (e.g., specific speakers, singing...). These elements will be randomly distributed while preserving the original speech durations and times of day. A tracking system will record daily details of each child's exposure duration to:

1. The mother's speech.
2. The speech of the surroundings.
3. Moments without speech.
4. The total duration of sound broadcasting (in case the system is stopped).

### **Measuring Language Outcomes**

WP3 includes three experiments on prosody development, one vocabulary measure, and one general cognitive development measure over five months.

#### **Testing Intervals:**

Infants will be tested at 7.5, 9, 10.5, and 12 months (see Fig. 2), as delays are detectable at these ages. This longitudinal design will highlight pathways of early speech perception, crucial for studying atypical development.

[figure not shown]

Fig. 2. Summary of testing points.

#### **Participants:**

See WP2 for participant details.

**SHORT TITLE/ACRONYM**

**Methods and Experiments:**

Three experiments will investigate key aspects of prosody using the well-established head-turn preference and central fixation procedures (see Fig.3).

1. **Lexical Stress** – This experiment will explore infants' increasing ability to process native sounds, specifically their preference for the most frequent first-syllable stress (trochaic pattern). Infants will hear disyllabic words stressed on either the first syllable (e.g., "gentle") or the second syllable (iambic pattern, e.g., "comply").
2. **Lexical Tone** – This experiment examines infants' declining ability to process non-native sounds. Infants will be exposed to Cantonese tones instantiated on the syllable "chee" produced by a female native speaker with either the rising tone 25 (此 'this; thus'; 始 'start') or the middle level tone 33 (次 'next'; 刺 'thorn').
3. **Prosodic Boundaries** – This experiment will assess infants' sensitivity to sentence-level prosody, specifically prosodic boundaries. Infants will be presented with two versions of a sentence: one well-formed (e.g., "John doesn't know what rabbits eat. Leafy vegetables taste so good") and one ill-formed with unnatural phrase breaks (e.g., "what rabbits eat. Leafy vegetables taste"). Sensitivity to prosodic boundaries at 6 months has been linked to vocabulary development at 24 months, and this study will investigate whether this can predict vocabulary scores at 12 months in preterm infants.

**SHORT TITLE/ACRONYM**

[figure not shown]
Lexical Tone		Lexical Stress	Prosodic Boundaries
Method	Central Fixation Procedure (CFP)	Head-turn Preference Procedure (HPP)	
Visual Stimuli			
Auditory Stimuli	
Two Cantonese lexical tone contrasts: Tone 25 vs 33
 
Instantiated on a CV syllable pronounced “chee”
	
192 disyllabic English words:
 
 
96 with a weak-strong syllable accent
 
96 with a strong-weak syllable accent
 
	
4 English sentences:
 
2 well-formed prosodic sentences 2 prosodically ill-formed sentences
 
Two English passages

Familiarization Phase	30s Tone 25 or 33	4 music trials	
2 versions of the same sequence:
 
 
One prosodically well-formed (bold)
 
One prosodically ill-formed (italics)
 
 
John doesn't know what rabbits eat. Leafy vegetables taste so good. They don't cost much either.

Test Phase	
8 trials:
 
 
4 Alternating (i.e., 25 33 25 33 ... or 33 25 33 25 ...)
 
4 Non-Alternating (i.e., 25 25 25 25... or 33 33 33 33...)
 
	
16 trials :
 
 
8 weak-strong lists with 12 words each (e.g., comply, befall, depart...)
 
8 strong-weak lists with 12 words each (e.g., pliant, falter, comet...)
 
	
2 passages:
 
 
One including the well-formed sentence.
 
The other including the ill-formed sequence.
 

Fig. 3. Summary of proposed methods.

**Vocabulary:** The Oxford Communicative Development Inventory (O-CDI), a parental questionnaire, will track infants' word comprehension and production at each time point.

**Cognitive Development:** The Bayley Scales will assess broader cognitive development at 7.5, and 12 months.

**Experiment Duration:** Each experiment will last approximately 5 minutes, with each visit lasting around one hour to allow parents time to complete the O-CDI and provide infants with breaks between experiments to minimise fatigue.

**SHORT TITLE/ACRONYM**

**Predictions:** Based on previous findings Preterm groups are expected to show delayed acquisition of these properties compared to the full-term group. If, as predicted, the delay stems from a lack of prenatal prosody exposure, the delay will appear in the Standard-Care-group but not in the Womb-Simulated-group.

**Analyses:** Data on looking times, vocabulary, and cognitive development will be collected and compared across the three study groups. Analyses will be conducted using linear mixed-effects models, which are particularly suitable for handling missing data in longitudinal studies with repeated measurements.

Analyses will be conducted using R and the lme4 package to fit linear mixed-effects models. Fixed effects will include Group (womb-simulated preterm, standard-care preterm, full-term), Age (7.5, 9, 10.5, 12 months), and Stimulus Type (e.g., alternating vs. non-alternating). Participants and stimuli will be included as random effects. Model selection will follow a stepwise comparison approach, retaining the model with the lowest BIC and a significant log-likelihood ratio test. A typical model will take the form:

`lmer(TotalLook~Group*Age*StimType+(Age|SubjectID)+(1|Stimulus)).`

P-values will be derived from F-values using the Satterthwaite approximation. Planned comparisons will use orthogonal contrasts. While SES, gestational age, and birth weight will not be included in the primary models, their effects will be explored in secondary analyses. All analyses will be pre-registered and conducted in line with open science practices.

Data will be summarised using descriptive statistics and visualised with graphs to illustrate group differences and developmental trajectories. Demographic matching of full-term infants will further strengthen causal inference by reducing potential confounding factors.

**Dissemination Activities:** Co-designed resources such as infographics, videos, animations, and a website will target families and practitioners. Workshops for families, practitioners, and

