### **2.1 Objectives**

- Design and implement a womb-like acoustic environment in the NCU using parental voice recordings and simulated sounds from the womb.
- Evaluate its effects on language development, including prosody, vocabulary acquisition, and cognitive development, comparing preterm infants exposed to the womb-like environment with those receiving standard care and full-term infants across their first year of life

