## **Implementing Womb-like Environments in NCUs**

**SHORT TITLE/ACRONYM**

Final outputs will be implemented and tested in incubators, initially without infants (as part of WP1). Once extensively tested, the system will be introduced to incubators with infants having parental consent.

Participants. A total of 150 infants will be tested, accounting for a 20% attrition rate due to multiple experiments (10%) and longitudinal design (10%). This ensures sufficient participants per group (WS-PTg, SC-PTg, CO-FTg) for statistical analyses ( $\alpha=0.05$ , power=0.80, GPower 3.1). The estimate is based on effect sizes ( $d=0.59-0.80$ ) from prior studies on early speech perception and language outcomes in preterm infants. Participants will include:

- 1) Womb-simulated PT group (WS-PTg): Forty healthy preterm infants meeting five primary criteria:
  1. Gestational age  $\geq 26$  and  $\leq 34$  weeks.
  2. Absence of major cerebral damage (e.g., periventricular leukomalacia, intraventricular haemorrhage...).
  3. No indication of visual or hearing impairment.
  4. No family risks of developmental or language disorders.
  5. From monolingual English-speaking families.

Infants eligible to participate in the WS-PTg will be identified by the NCU team as soon as possible after their arrival to the unit and parents of these infants will be approached by one of the neonatal nurses to ask if they would want to take part in the project. Families who have given consent will be approached by the research team and given the necessary equipment to do the audio recordings. Meanwhile, a general recording of infant-directed speech recorded by the research team will be used until parental recordings are available. Infants will be exposed to the recordings until they are discharged from the NCU or they reach their due date.

- 2) Standard care PT group (SC-PTg): Forty healthy preterm infants who meet the same criteria outlined above will be recruited using the same strategy. Infants assigned to the SC-PTg will, when possible, be those who have already been discharged from the NCU.
- 3) Comparison FT group (CO-FTg): Forty healthy full-term infants born at  $\geq 37$  weeks who also meet criteria 2–5 outlined above.

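### Orthogonal contrasts cannot hold both comparisons in the objective or both halves of the prediction, and the stated difference tests cannot show that the womb-simulated group has no delay

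*Protocol*

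**What the plan says.** The objective in Protocol section 2.1 is to evaluate effects by "comparing preterm infants exposed to the womb-like environment with those receiving standard care and full-term infants across their first year of life". That is two comparisons: WS with SC, and WS with FT.

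The Predictions paragraph of section 3 begins with "Preterm groups are expected to show delayed acquisition of these properties compared to the full-term group". It then gives the result expected if missing prenatal prosody is the cause: "the delay will appear in the Standard-Care-group but not in the Womb-Simulated-group". Read as group comparisons, this is SC-FT present and WS-FT absent.

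The Analyses paragraph of section 3 fits a mixed model with Group, Age and Stimulus Type and their interactions. On inference it says "P-values will be derived from F-values using the Satterthwaite approximation" and "Planned comparisons will use orthogonal contrasts". The contrasts are not listed, no contrast is singled out as the test of benefit, and no criterion is given for concluding that a delay is absent.

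The Participants text in section 3 gives 40 infants per group, 150 in total after allowing for 20% attrition, effect sizes of d=0.59-0.80, alpha 0.05 and "power=0.80, GPower 3.1".

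**The concern.** There are two separate difficulties.

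The first concerns the contrast rule. Three groups carry two degrees of freedom, so an orthogonal set has at most two contrasts. The objective and the prediction each need a pair of pairwise comparisons. If no such pair is orthogonal, the method written into the protocol cannot deliver what the protocol sets out to compare.

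The second concerns the form of the hypothesis. Half of the predicted result is an absence of difference, while the only inference described is tests of difference. A significant SC-FT beside a non-significant WS-FT neither tests WS against SC nor shows that WS equals FT. At this sample size the pattern can arise by chance, or when the intervention only partly works. The findings are meant to inform neonatal care (section 2.2), so the test on which a claim of benefit rests should be fixed before pre-registration.

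**Working it through.** **Inputs.** From Protocol section 3: 40 per group, total 150, attrition 20%, d=0.59-0.80, alpha 0.05. Assumed here: two-sided testing (sidedness is not stated) and one cross-sectional comparison of group means with SD 1. The planned model uses repeated looking times at four ages, and the document gives no variance components for it.

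**The plan's own figure.** 3 × 40 = 120, and 120/(1 − 0.20) = 150. It reproduces.

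**Orthogonality.** Coefficients in the order (WS, SC, FT):
- WS-SC · WS-FT = (1,−1,0)·(1,0,−1) = 1
- WS-SC · SC-FT = (1,−1,0)·(0,1,−1) = −1
- WS-FT · SC-FT = (1,0,−1)·(0,1,−1) = 1

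None is zero. Two relevant orthogonal sets do exist:
- Set A: WS-SC with the preterm average against FT, (1,−1,0)·(½,½,−1) = 0. A contrast orthogonal to WS-SC must weight WS and SC equally, so this partner is the only one up to scale.
- Set B: WS-FT with SC against the average of WS and FT, (1,0,−1)·(½,−1,½) = 0.

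**Set A if the intervention fully works** (WS = FT, SC delayed by d).
- WS-SC: SE = sqrt(2/40) = 0.224; power 0.74-0.75 at d=0.59 and 0.94-0.95 at d=0.80 (t and normal calculations).
- Preterm average against FT: the contrast equals d/2 and SE = sqrt(1/80 + 1/40) = 0.194. At d=0.59, z = 0.295/0.194 = 1.52, power 33%. At d=0.80, z = 0.40/0.194 = 2.07, power 54%.

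**Set B.** If the intervention fully works, SC against the average of WS and FT has power 0.86 at d=0.59 and 0.98 at d=0.80. If it does nothing (WS and SC both delayed by d), the contrast is still d − d/2 = d/2, and its SE is sqrt(1.5/40) = 0.194. The z-values are again 1.52 and 2.07, so it is significant about 33% to 54% of the time with no benefit. It cannot serve as the test of benefit.

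**Judging the pattern from two tests.** The SC-FT and WS-FT statistics share the FT mean, so their correlation is (1/40)/(2/40) = 0.5. The probability that SC-FT is significant and WS-FT is not, from the bivariate normal distribution:

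| True delay SC / WS | Pattern appears | WS-FT non-significant |
|---|---|---|
| 0.59 / 0.59 (no benefit) | 0.13 | 0.26 |
| 0.80 / 0.80 (no benefit) | 0.04 | 0.06 |
| 0.59 / 0.295 (half remains) | 0.51 | 0.74 |
| 0.80 / 0.40 (half remains) | 0.52 | 0.58 |

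Simulation with 200,000 runs gave 0.129, 0.039 and 0.508 for the first three rows. With no benefit, a two-sided 0.05 test of WS-SC is significant in the favourable direction 2.5% of the time.

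**What 40 per group can say about no delay.** The WS-FT 95% CI half-width is 1.99 × 0.224 = 0.445 SD. The probability that the 95% CI lies inside ±m when the true difference is zero is 2Φ(m/0.224 − 1.96) − 1 (set to 0 where negative), by normal approximation. The margins are assumed, since the document gives none: 0 at m=0.40, 0.22 at 0.50, 0.50 at 0.59 and 0.89 at 0.80.

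**The case against.** The best defence is that orthogonal contrasts do not prevent a test of benefit. Set A contains WS-SC, with useful power. That stands: a reader might infer that the stated method cannot test the intervention at all, and the algebra does not support this. What remains is narrower. Choosing Set A gives up both comparisons with FT as separate tests and replaces them with an average of exposed and unexposed infants.

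Set B has high power for the predicted shape. It also rejects often when the intervention does nothing, so it does not rescue the rule.

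A reader might also infer that a non-significant WS-FT result will be reported as normalisation. The protocol says no such thing. The sentence is a conditional prediction, not a success rule, and sections 2 and 2.1 speak of comparing the groups directly. The pattern rates above therefore describe a risk if the prediction were read that way, not a stated procedure.

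Naming contrasts and setting a margin are often left to an analysis plan or the promised pre-registration, and silence on them alone would be no finding. Here, however, the protocol does fix a rule, and the rule does not fit its own objective.

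Finally, no-benefit pattern rates of 16-17% can be obtained, but only with delays of about 0.40-0.50, below the protocol's range. Within d=0.59-0.80 the rate is 13% falling to 4%.

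**Conclusion.** The concern holds in this limited form. Orthogonal contrasts cannot carry both comparisons in the objective or both halves of the prediction, and tests of difference cannot establish that WS has no delay. The orthogonal partner of WS-SC has only 33-54% power when the intervention fully succeeds. If the predicted pattern were judged from two separate tests, it would appear in about 13% to 4% of trials with no benefit, against 2.5% for a favourable WS-SC test, and in 51-52% when half the delay remains.

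The non-orthogonality is exact. The percentages rest on 40 analysable infants per group, a single comparison of means with SD 1, and two-sided 0.05. They indicate size and are not operating characteristics of the mixed model. It is not shown that the plan cannot test benefit, or that it will treat non-significance as equality. This should be changed before pre-registration.

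**What to change.** In the Analyses paragraph of section 3, replace the orthogonal-contrast sentence with three named pairwise contrasts on the relevant Group-by-Stimulus-Type effect:

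- WS-SC: the sole basis for a claim of benefit.
- SC-FT: the check that a delay exists to be closed.
- WS-FT: an estimate with its 95% CI, with no delay claimed only if the CI lies inside a margin set in the pre-registration.

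Reword the prediction to match: SC is delayed relative to FT, and WS is less delayed than SC. This also removes the tension with the preceding sentence, which expects the preterm groups in general to be delayed.

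The cost is wording in the protocol and pre-registration, with no extra infants or visits. The three contrasts are correlated, which does no harm when one is designated as deciding. The real downside is that equivalence of WS to FT will probably not be shown at 40 per group unless the margin is wide. For 80% probability that the 95% CI lies inside the margin when the true difference is zero, the numbers needed are 85 per group at 0.50 SD, 61 at 0.59 and 33 at 0.80 (assumed margins). The margin should be chosen on developmental grounds, not to fit the sample.

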## **5 SAMPLE AND RECRUITMENT**

### **5.1 Eligibility and Inclusion Criteria**

Preterm Group

1. Gestational age  $\geq 26$  and  $\leq 34$  weeks.
2. Absence of major cerebral damage (e.g., periventricular leukomalacia, intra-ventricular haemorrhage...).
3. No indication of visual or hearing impairment.
4. No family risks of developmental or language disorders.
5. From monolingual English-speaking families.

Full-term Group

1. Gestational age  $\geq 37$  weeks.
2. Absence of major cerebral damage (e.g., periventricular leukomalacia, intra-ventricular haemorrhage...).
3. No indication of visual or hearing impairment.

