### **5.1.1 Exclusion criteria**

#### **Preterm infants**

- Infants will be excluded from the study if they meet any of the following criteria:
- Born before 26 weeks' gestation or after 34 weeks' gestation.
- Evidence of major brain injury or neurological damage, including but not limited to periventricular leukomalacia or intraventricular haemorrhage.
- Known or suspected hearing impairment or visual impairment.
- Presence of diagnosed genetic, neurological, developmental, or language disorders, or a known family history of developmental or language disorders that may affect language development.
- Infants from bilingual or multilingual households, or where English is not the primary language spoken to the infant at home.
- Medical instability or clinical concerns identified by the neonatal care team that would make participation inappropriate or place additional burden on the infant or family.

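### The mixed model has no family level although twins may enrol; if co-twins share a preterm group, standard errors for between-infant contrasts are too small

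*Protocol*

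**What the plan says.** The Analyses text in Section 3 (under Measuring Language Outcomes) applies linear mixed-effects models to all outcomes: "Data on looking times, vocabulary, and cognitive development will be collected and compared across the three study groups". It then sets the random part: "Participants and stimuli will be included as random effects". The formula, introduced with "A typical model will take the form", has a random intercept and age slope by infant and a random intercept by stimulus. No family or pregnancy level appears there or elsewhere. Models are chosen stepwise by lowest BIC with a significant likelihood ratio test. SES, gestational age and birth weight are kept out of the primary models.

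The womb-simulated group is "Forty healthy preterm infants meeting five primary criteria", and the standard-care group uses the same criteria. One of these concerns the family ("From monolingual English-speaking families"), but none limits how many infants a family may contribute. The list in Section 5.1.1 that opens "Infants will be excluded from the study if they meet any of the following criteria" does not mention multiples. Twins, multiples and siblings are not mentioned under recruitment, group assignment, sample size or analysis.

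Vocabulary is measured with "The Oxford Communicative Development Inventory (O-CDI), a parental questionnaire" at every visit, and the Bayley Scales are given at 7.5 and 12 months.

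**The concern.** Both preterm groups consist of infants born at 26 to 34 weeks, a population in which multiple births can be expected (an assumption; the protocol gives no figure). Co-twins share parents, SES, gestational age and home speech. They probably also share the parent who completes the O-CDI. Since SES and gestational age are left out of the primary models, that shared variation stays in the between-infant variance.

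The written model gives each infant a separate, independent random effect. If co-twins sit in the same group, their positive correlation increases the true variance of the group mean, and the model does not see it. At stake are the confidence interval and the 0.05 error rate for the contrast of most interest, womb-simulated versus standard care, on vocabulary and cognition.

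**Working it through.** **The plan's own figure.** Three groups of 40 make 120, and 120/(1 − 0.20) = 150, the stated total. This counts infants, with no allowance for families.

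**Inputs.** From the protocol: n = 40 per group, alpha = 0.05 (taken as two-sided; the protocol does not say). Assumed, because the documents give neither: share p of preterm infants enrolled with a co-twin, 20–30%; within-pair correlation ICC, 0.3–0.8. At n = 40 this share means 8–12 infants, or 4–6 pairs, per preterm group.

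**Co-twins in the same group.** Each paired infant adds one covariance term, so the variance of a group mean is (σ²/n)(1 + p × ICC). The formulas are:

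- Design effect, womb-simulated versus standard care: DE = 1 + p × ICC
- Design effect, preterm versus full-term, with clustering on one side only: DE = 1 + p × ICC/2
- Understatement of the SE: 1 − 1/√DE
- Type I error: 2 × (1 − Φ(1.96/√DE))
- Effective group size: 40/DE

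| p | ICC | DE, preterm v preterm | SE understated | Type I error | Effective n | Type I error, preterm v full-term |
|---|---|---|---|---|---|---|
| 20% | 0.3 | 1.06 | 2.9% | 5.7% | 37.7 | 5.3% |
| 20% | 0.5 | 1.10 | 4.7% | 6.2% | 36.4 | 5.6% |
| 20% | 0.8 | 1.16 | 7.2% | 6.9% | 34.5 | 5.9% |
| 30% | 0.3 | 1.09 | 4.2% | 6.0% | 36.7 | 5.5% |
| 30% | 0.5 | 1.15 | 6.7% | 6.8% | 34.8 | 5.9% |
| 30% | 0.8 | 1.24 | 10.2% | 7.8% | 32.3 | 6.4% |

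A simulation of infant-level t-tests (40 per group, 40,000 replicates) agrees. At 20% and 0.5 the type I error was 6.2%, and at 30% and 0.5 it was 6.8%.

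**Co-twins split between the two preterm groups.** The covariance now reduces the variance of the difference, so DE = 1 − p × ICC. At 20% and 0.5, √0.90 = 0.95 and simulated type I error is 3.9%: the model SE is too large. With no co-enrolled pairs, DE = 1 and there is no error.

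**Which contrasts.** O-CDI and Bayley scores and mean looking time are compared between infants, so the table applies to them. The prosody predictions rest on Group x StimType, a within-infant difference between two stimulus types. A shared family level enters both terms of that difference and cancels. Its SE is affected only if co-twins also correlate in the size of their preference.

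**The case against.** The strongest objection is that handling of siblings is usually left to a statistical analysis plan. The formula is offered only as typical, and all analyses are to be pre-registered. Part of this stands, since a later document could add a family term. But the protocol does more than stay silent: it names the random effects and writes the model out. It also fixes detailed eligibility lists that let co-twins in. An analysis run as written would treat them as independent.

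The second objection is that everything depends on assumed inputs. A co-twin matters only if also eligible, consented and retained over four visits, and the top of the range needs a correlation of 0.8, for which no source is at hand. This stands. It is why the finding is conditional and the mid-range result is modest.

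The third concerns direction. A reader might infer that standard errors are too small in every preterm contrast. The documents do not support that. No rule keeps co-twins in one group, and split pairs reverse the error. Same-group placement is only likely: groups are not randomised, families rather than infants receive the recording equipment, and standard-care infants are, when possible, those already discharged. The prosody contrasts escape unless preferences themselves correlate.

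The fourth is that one extra model term may seem a complete cure. It is not. A family intercept leaves Group x StimType essentially unchanged, and with 4–6 pairs per preterm group the stated BIC rule could drop it. The text does not say whether that rule covers random effects. If it does, simulation with 40 per group (1,500 replicates) keeps the term in roughly 9–12% of runs at ICC 0.3, 23–33% at 0.5 and 78–94% at 0.8. At 0.3 the family variance is estimated as zero in about 17–24% of runs.

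**Conclusion.** The point holds conditionally. The model as written has no family level, the criteria admit multiples, and any co-twins enrolled in the same preterm group would be counted as independent infants. For between-infant contrasts of womb-simulated versus standard care, two-sided type I error would be about 5.7–7.8%, and about 6.2–6.8% at a correlation of 0.5. Preterm versus full-term contrasts would be inflated about half as much.

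These figures rest on two assumptions (20–30% of preterm infants in pairs, correlation 0.3–0.8) and on same-group placement, which is likely but unstated. It does not follow that the standard errors are known to be wrong, that the error always runs one way, or that the prosody contrasts are affected. The size is modest at mid-range values. It still merits correction before pre-registration, because the remedy is cheap and the family link may be hard to recover later: Sections 6 and 7.6 separate identifiable from research data and provide for an anonymised public archive.

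**What to change.** - State whether multiples may enrol and whether co-twins stay in one group.
- Record a FamilyID at consent and carry it in pseudonymised form into the research dataset.
- Add a family random intercept, with SubjectID nested in FamilyID, to the O-CDI and Bayley models. Keep it as a design term, outside the BIC selection step.
- Use family-clustered standard errors where that fit is singular, and for the looking-time Group x StimType contrasts, where a family intercept does not help.
- Report the number of families as well as infants in each group.

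The cost is one identifier, one model term and a few lines in the pre-registration. The downside is slightly wider intervals. No infant need be excluded.

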**SHORT TITLE/ACRONYM**

Sample size calculations were informed by prior research on early speech perception and language development in preterm infants, which report medium to large effect sizes ( $d = 0.59\text{--}0.80$ ). Power calculations ( $\alpha = 0.05$ , power = 0.80) conducted using G\*Power (version 3.1) indicate that this sample size is adequate to detect meaningful group differences in language and cognitive outcomes. This sampling strategy directly addresses the study's aim of identifying whether early auditory experience influences language development trajectories.

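### Stepwise selection by BIC is not barred from removing the Group-by-Stimulus-Type terms that carry the looking-time hypothesis, and BIC sets a stricter bar than the 0.05 behind the sample size

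*Protocol*

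**What the plan says.** The Analyses paragraph of section 3 lists Group, Age and Stimulus Type as fixed effects, with participants and stimuli as random effects. It then sets a decision rule: "Model selection will follow a stepwise comparison approach, retaining the model with the lowest BIC and a significant log-likelihood ratio test". The formula that follows is offered as a typical form, not as the fixed analysis model: "lmer(TotalLook~Group*Age*StimType+(Age|SubjectID)+(1|Stimulus" (closing brackets omitted here). Inference is described in two sentences: "P-values will be derived from F-values using the Satterthwaite approximation" and "Planned comparisons will use orthogonal contrasts". All analyses are to be pre-registered.

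The Predictions paragraph just before it says that, if the hypothesis is right, "the delay will appear in the Standard-Care-group but not in the Womb-Simulated-group".

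The sample size (section 3, Participants, and section 5.2.1) rests on alpha 0.05, power 0.80 and effect sizes of d=0.59 to 0.80. Section 5.2.1 says that the power calculations "indicate that this sample size is adequate to detect meaningful group differences in language and cognitive outcomes". Neither place mentions a selection step.

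**The concern.** In the three looking-time experiments the outcome is looking time to one stimulus type against another. A group difference in total looking time does not show a prosodic delay. What shows it is a difference between groups in the effect of stimulus type, that is, the Group-by-StimType term, possibly changing with Age. The protocol commits to the three main effects but protects no interaction, so the rule followed as written can remove the term that answers the question.

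The two parts of the rule also differ in strictness. A likelihood-ratio test at 0.05 and a BIC comparison disagree over a wide range of results. Because both must be satisfied, BIC decides. A Group-by-StimType term with a likelihood-ratio p-value of 0.01 would be discarded under every row count examined below. If the term survives, its Satterthwaite p-value takes no account of the hurdle it passed, and an estimate that had to clear a high hurdle tends to be too large.

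**Working it through.** **Inputs.** 40 infants in each of three groups after attrition, 120 in all, and four ages (section 3). Fig. 3 gives 8 test trials for lexical tone and 16 for lexical stress. Assumptions: each task is run at all four ages (Fig. 2 is not shown), the likelihood-ratio test uses 0.05 (no level is stated), and n in BIC is the number of data rows. The case n = number of infants is shown as well.

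**The plan's own figure.** 120/(1 - 0.20) = 150, as stated. The test behind the power claim is not named. A two-sided two-sample t-test with 40 per group has power 0.74 at d=0.59 and 0.94 at d=0.80. A three-group ANOVA with f = d/2 = 0.295 and N=120 has 0.82. So 80% is reached within the stated range of d.

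**BIC cut-off.** BIC = -2 log L + k ln(n). A term with df parameters lowers BIC only if its likelihood-ratio chi-square exceeds df x ln(n). Group-by-StimType has (3 - 1) x (2 - 1) = 2 df. For 2 df the upper tail is exp(-x/2), so the nominal level is exp(-ln n) = 1/n. The ordinary 0.05 cut-off is 5.99.

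**Power kept.** A 2-df chi-square test with exactly 80% power at 0.05 has non-centrality 9.63. The last column gives the probability that such a test exceeds the BIC cut-off.

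| How n is counted | n | Cut-off 2 ln(n) | Nominal level | Power kept |
|---|---|---|---|---|
| Stress, trial rows: 120 x 4 x 16 | 7,680 | 17.89 | 0.00013 | 16% |
| Tone, trial rows: 120 x 4 x 8 | 3,840 | 16.51 | 0.00026 | 21% |
| One row per infant, age and stimulus type: 120 x 4 x 2 | 960 | 13.73 | 0.0010 | 33% |
| Infants | 120 | 9.57 | 0.0083 | 57% |

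**Power at the protocol's effect sizes.** Suppose womb-simulated equals full-term and standard care is lower by d. The group means 0, 0, -d deviate from their average by d/3, d/3 and -2d/3, so the non-centrality is 40 x (2/3) x d², which is 9.28 at d=0.59 and 17.07 at d=0.80.

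- If d describes the whole information in the test, power at 0.05 is 78% and 97%. Under the trial-row cut-offs it is 15-19% and 51-58%.
- If the information is worth two independent ages (non-centrality doubled), power under the cut-offs is 58-64% and 96-97%.
- If d holds at each of four ages, treated as independent and pooled (non-centrality 37.1 at d=0.59), it is about 98% at d=0.59 and close to 100% at d=0.80.

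**Three-way term.** With Age categorical it has 6 df, and the cut-offs are 6 ln(3,840) = 49.5 and 6 ln(7,680) = 53.7, nominal levels below 1e-8. With Age linear it has 2 df and the table applies. The protocol does not say which is meant.

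**The case against.** Four points on the other side have weight.

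**Scope of the selection.** The rule may have been meant for the random effects only, and the full interaction is the model shown straight after it. The planned orthogonal contrasts are nowhere made conditional on selection. A reader might infer that the hypothesis will be dropped untested. The text does not say that. But it does not exclude it either: it guarantees only main effects, and it does not say how a contrast on stimulus type would be obtained if the interaction were removed.

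**Size of the power loss.** A reader might infer that the rule destroys the planned 80% power. The low figures at d=0.59 pair the rows of all four ages with the information of a single test. If d=0.59 holds at every age and all are pooled, power stays near 98%. The protocol does not say which contrast, age or score d refers to, so neither end can be claimed. A delay confined to one age would do worse: in simulation with no between-infant variation in preference, the pooled term passed in about 1% of runs at d=0.59. Averaging over four ages explains much of that, since its power at 0.05 was already only 25%.

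**The level is nominal.** A reader might infer that 0.05 is simply replaced by 0.0001 to 0.0003, making the analysis conservative. That range applies only to a 2-df term with trial rows at four ages. It also need not be the true error rate, because the typical model has no by-infant slope for stimulus type. In simulation with 20-50% of the preference-score variance lying between infants, false retention was about 1-16%.

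**Other outcomes and documents.** Vocabulary and Bayley scores have no stimulus-type factor, and their overall group comparison is a listed main effect, so these figures do not carry over to them. The pre-registration may add detail. That does not cure a rule which the protocol already states and which a pre-registration could copy.

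**Conclusion.** The concern holds in limited form. As written, the rule allows the terms that carry the looking-time hypothesis to be removed by a criterion stricter than the alpha behind the sample size. The direction does not depend on how rows are counted: the nominal 2-df level runs from 0.00013 to 0.008, and a test planned at exactly 80% power keeps between 16% and 57%. The size does depend on assumptions: tasks run at all four ages, the count that BIC uses for n, and what d refers to. At d=0.59 with trial rows, power could be about 15% or about 98%. The protocol does not support a general statement that power is lost, or that the three-way term would almost never survive; the latter requires Age to be categorical. Whatever the power, p-values computed after this selection do not account for it.

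**What to change.** In the Analyses paragraph of section 3, and in the pre-registration, state that the Group*Age*StimType fixed effects and the planned womb-simulated versus standard-care contrast on stimulus type are set in advance, exempt from BIC and likelihood-ratio selection, and tested at the stated alpha. State also whether Age is categorical or linear. Limit any simplification to the random-effects structure, in a pre-specified order, and only for non-convergence. In section 5.2.1, say which contrast, score and ages d=0.59 to 0.80 describes, so that the power claim refers to the test that will be run.

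This costs a few sentences and no data. The downside is a slightly larger model that keeps some non-significant terms.
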